**Appendix 5: Expected adverse event frequencies based on MISTIE II trial data.**

Event	% Events (n=573)
Blood and lymphatic system disorders	3.14%
Anemia	2.27%
Leukocytosis	0.87%
Cardiac disorders	5.89%
Atrial fibrillation	0.87%
Atrial flutter	0.35%
Bradycardia	0.52%
Cardiac arrest	0.70%
Chest pain	0.35%
Congestive heart failure	0.17%
Dysrhythmia	0.17%
Myocardial infarction	0.52%
Prolonged QT interval on EKG	0.17%
Pulmonary vascular congestion	0.17%
PVC's; bigeminy	0.17%
Sinus bradycardia	0.17%
Sinus tachycardia	0.52%
Supraventricular tachydysrhythmia	0.52%
Ventricular extrasystoles	0.17%
Ventricular fibrillation	0.35%
Endocrine disorders	0.17%
Hypothyroid	0.17%
Eye disorders	0.17%
Vision abnormalities	0.17%
Gastrointestinal disorders	5.89%
Abdominal pain	0.35%
Colitis	0.17%
Constipation	1.22%
Diarrhea	0.87%
Dysphagia	0.70%
Esophagitis	0.17%
Gall bladder thickening	0.17%
Gastritis	0.17%
Gastrointestinal bleeding	0.70%
Ileus	0.17%
Increased gastric outputs	0.17%
Intraoperative hemorrhage (PEG)	0.17%
Peptic ulcer	0.17%
Rotten tooth extraction	0.17%
Small intestine infection	0.17%
Vomiting	0.35%
General disorders and administration site conditions	6.44%

Death due to index bleeding event	1.05%
Fever	4.19%
Generalized edema	0.17%
Localized edema	0.52%
Phlebitis	0.17%
Sudden death NOS	0.17%
Transient arm weakness	0.17%
Immune system disorders	0.35%
Anaphylaxis	0.17%
Angioedema	0.17%
Infections, non-neurologic	7.13%
Bacteremia	0.87%
Bronchial infection	0.17%
Clostridium difficile	0.35%
Endocarditis	0.17%
Enterocolitis infectious	0.35%
Pleural infection	0.17%
Sepsis	0.52%
Sinusitis	0.35%
Skin infection	0.17%
Upper respiratory infection	0.52%
Urinary tract infection	3.32%
Vaginal infection	0.17%
Investigations	2.57%
Coagulopathy	0.17%
Creatinine increased	0.17%
Eosinophilia	0.17%
Increased ALT	0.17%
Increased AST	0.17%
Increased bilirubin, direct	0.17%
Increased chloride	0.17%
increased d-dimer	0.35%
Increased fibrinogen	0.35%
Increased PT	0.17%
Platelet count decreased	0.17%
Thrombocytopenia	0.17%
Thrombocytosis	0.17%
Metabolism and nutrition disorders	11.67%
Acidosis (metabolic or respiratory)	0.35%
Dehydration	0.17%
Electrolyte imbalance	0.17%
Hyperglycemia	1.22%
Hyperkalemia	0.52%
Hypematremia	0.70%

Hypertension	2.44%
Hypoalbuminemia	0.17%
Hypocalcemia	1.05%
Hypoglycemia	0.87%
Hypokalemia	1.40%
Hypomagnesemia	0.70%
Hyponatremia	0.87%
Hypophosphatemia	0.87%
Metabolic alkalosis	0.17%
Musculoskeletal and connective tissue disorders	0.17%
Back pain	0.17%
Nervous system disorders	27.71%
Anoxic brain injury	0.17%
Aphasia	0.35%
CSF leak	0.17%
Depressed level of consciousness	1.92%
Dizziness	0.17%
Edema cerebral	0.87%
Headache	1.57%
Herniation	0.17%
Hydrocephalus	0.35%
Intracranial hemorrhage: Catheter Tract, Enlargement	0.70%
Intracranial hemorrhage: Catheter Tract, New	4.01%
Intracranial hemorrhage: Hematoma, subdural	0.17%
Intracranial hemorrhage: Tissue, Enlargement	4.01%
Intracranial hemorrhage: Tissue, New	1.40%
Intracranial hemorrhage: Ventricular system, Enlargement	1.75%
Intracranial hemorrhage: Ventricular system, New	1.57%
Intracranial hypertension	1.75%
Ischemia cerebrovascular	1.92%
Mass effect	0.17%
Meningitis	0.17%
Muscle twitching	0.70%
Seizure	2.27%
Somnolence	0.17%
Stroke	0.17%
Syncope	0.70%
Ventriculitis, non-bacterial	0.17%
Wound reclosure after serous fluid leak	0.17%
Psychiatric disorders	1.04%
Agitation	0.87%

Labile sleep wake cycle	0.17%
Renal and urinary disorders	2.61%
Acute kidney injury	0.35%
Acute renal insufficiency	0.87%
Hematuria	0.35%
Left renal mass	0.17%
Urinary incontinence	0.17%
Urinary retention	0.70%
Respiratory, mediastinal and thoracic disorders	19.84%
Adult respiratory distress syndrome	1.22%
Aspiration	1.22%
Atelectasis	0.87%
Bronchospasm	0.17%
Dyspnea	0.17%
Epistaxis	0.87%
Hemothorax	0.17%
Hypoxemia	0.70%
Increased respiratory secretions	0.17%
Lung infection	1.22%
MRSA infection	0.17%
Pleural effusion	1.05%
Pneumonia	5.76%
Pneumothorax	0.17%
Pulmonary edema	0.70%
Respiratory arrest	0.17%
Respiratory failure	3.14%
Shortness of breath	0.35%
SIADH	0.17%
Stridor	0.17%
Tachypnea	0.52%
Tracheal stricture	0.17%
Tracheitis	0.35%
Wheezing	0.17%
Skin disorders	0.35%
Rash maculo-papular	0.35%
Vascular disorders	4.02%
Hypotension	1.05%
Thromboembolic event	2.97%

**Appendix 6: Genentech Drug Safety: Safety Reporting FAX Cover Sheet****SAFETY REPORTING FAX COVER SHEET****Genentech Supported Research**

AE / SAE [contact]

Alternate [contact]

Genentech Study Number	
Principal Investigator	
Site Name	
Reporter name	
Reporter Telephone #	
Reporter Fax #	

Initial Report Date	[DD] / [MON] / [YY]
Follow-up Report Date	[DD] / [MON] / [YY]

Subject Initials (Enter a dash if patient has no middle name)	[ ] - [ ] - [ ]
--	-----------------

## Appendix 7: Abbreviation List

AAN:	American Association of Neurology	GOSE:	Glasgow Outcome Scale Extended
AANS:	American Academy of Neurological Surgery	GRE:	Gradient echo
ADL:	Activities of Daily Living	HIPAA:	Health Insurance Portability and Accountability Act
AE:	Adverse event	HOB:	Head of bed
AHA:	American Heart Association	hr, h, or hrs:	Hour(s)
AIC:	Akaike Information Criterion	HR:	Heart rate
aPTT:	Activated partial thromboplastic time	ICES:	Intraoperative CT guided Endoscopic Surgery for intracerebral hemorrhage trial
ASA:	Aspirin	ICH:	Intracerebral hemorrhage
ATACH:	Antihypertensive Treatment of Acute Cerebral Hemorrhage Trial	ICH:	International Conference on Harmonisation
AVM:	Arteriovenous malformation	ICP:	Intracranial pressure
BA:	Bioavailability	ICU:	Intensive care unit
BE:	Bioequivalence	IEC:	Independent Ethics Committee
BP:	Blood pressure	Inc:	Incorporated
CAPA:	Corrective and preventative action plan	IND:	Investigational new drug
cc:	Cubic centimeter	INR:	International normalized ratio
CCC:	Clinical Coordinating Center	INTERACT:	Intensive Blood Pressure Reduction in Acute Cerebral Haemorrhage Trial
CD:	Compact Disc	IRB:	Institutional Review Board
CES-D:	Center for Epidemiological Studies – Depression	IST:	Investigator sponsored trial
CFR:	Code of Federal Regulations	ITT:	Intention-to-treat
CHANT:	Cerebral Hemorrhage and NXY-059 Treatment	IV:	Intravenous
CI:	Confidence interval	IVH:	Intraventricular hemorrhage
CLEAR III:	Clot Lysis: Evaluating Accelerated Resolution of Intraventricular Hemorrhage: Phase III	JHMI:	Johns Hopkins Medical Institutions
cm:	Centimeter	JHU:	Johns Hopkins University
CRO:	Contract research organization	kcal:	Kilocalorie
CSF:	Cerebrospinal fluid	kg:	Kilogram
CT:	Computerized tomography	LOC:	Level of consciousness
CTA:	Computed tomography angiogram	LTF:	Lost to follow-up
CTCAE:	Common Terminology Criteria for Adverse Events	MAP:	Mean arterial pressure
CV:	Curriculum vitae	MD:	Doctor of Medicine
CVD:	Cardiovascular disease	med:	Medical
DBP:	Diastolic blood pressure	MedDRA:	Medical Dictionary for Regulatory Activities
DCC:	Data Coordinating Center	MEOI:	Medical event of interest
dCT:	Diagnostic Computed Tomography	mg:	Milligram
Diag:	Diagnostic	MHRA:	Medicines and Healthcare products Regulatory Agency
DICOM:	Digital imaging and communications in medicine	min:	minutes
DNI:	Do not intubate	MIS:	Minimally invasive surgery
DNR:	Do not resuscitate	MISTIE II:	MISTIE Phase II (precursor to MISTIE III)
DSMB:	Data Safety and Monitoring Board	MISTIE III:	Minimally Invasive Surgery plus rt-PA for ICH Evacuation Phase III
DVD:	Digital video disc	mL:	Milliliter
DVT:	Deep vein thrombosis	mmHg:	Millimeters of mercury
DWI:	Diffusion weighted imaging	MMSE:	Mini-Mental State Exam
EC:	Executive Committee	MOP:	Manual of Operations and Procedures
eCRF:	Electronic case report form	MR:	Magnetic resonance
ED:	Emergency Department	MRA:	Magnetic resonance angiogram
EDC:	Electronic data capture	MRI:	Magnetic resonance imaging
EKG:	Electrocardiogram	mRS:	Modified Rankin Scale
EOT:	End of treatment	MTI:M3	Mechanisms of Tissue Injury in MISTIE III (ancillary study)
EQ-5D:	Euroqol-5D	NIH:	National Institutes of Health
eTMF:	Electronic trial master file	NIHSS:	National Institutes of Health Stroke Scale
EUSI:	European Stroke Initiative	NINDS:	The National Institute of Neurological Disorders and Stroke
EVD:	Extraventricular drainage	OHRP:	Office of Human Research Protection
FAST:	Factor Seven for Acute Hemorrhagic Stroke Trial	OR:	Odds ratio
FDA:	Food and Drug Administration	OR:	Operating room
FFP:	Fresh frozen plasma	PACS:	Picture Archiving and Communication System
Fig:	Figure	PBSI:	Preference Based Stroke Index
G:	Gram	PHI:	Protected health information
GCP:	Good Clinical Practice	PI:	Principal investigator
GCP:	Good clinical practice	PT:	Prothrombin time
GCS:	Glasgow Coma Scale	Pts:	Patients
GEE:	Generalized estimating equations	Q:	Every
GLMM:	Generalized Linear Mixed Model	QA:	Quality assurance
gm:	Gram	QD:	Every day
GOS:	Glasgow Outcome Scale	QOL:	Quality of life
RDS:	Regulatory document specialist	RCT:	Randomized clinical trial
ROC:	Receiver Operating Characteristic	SIS:	Stroke Impact Scale
rt-PA:	Recombinant tissue plasminogen activator	SIS:	Stroke Impact Scale
SAE:	Serious adverse event	SOP:	Standard operating procedure
SAINT:	Stroke-Acute Ischemic NXY Treatment	SPRG:	Stroke Progress Review Group (NINDS Advisory and Peer Review Group)
SBP:	Systolic blood pressure	STICH:	Surgical Trial in Lobar Intracerebral Hemorrhage
SCDs:	Sequential compression devices	surg:	Surgical
SD:	Standard deviation	TIL:	Therapy intensity level
SDV:	Source document verification	t-PA:	Tissue plasminogen activator
SID:	Study identification number	VISTA:	Virtual International Stroke Trials Archive
		Vol:	Volume

## Appendix 8: MTI-M3 Ancillary Study Protocol

Participation in the MTI-M3 ancillary study is optional. Study centers outside of the US and Canada will not participate in the portion of the protocol that requires overnight shipment of samples to Yale University. Otherwise, all study centers are eligible to participate but may opt-out.

Mechanisms of Tissue Injury in MISTIE III: Rebleeding and inflammation: Predicting risk of excessive bleeding in minimally invasive surgery and inflammatory marker evaluation.

### 1. Abstract

Intracerebral hemorrhage (ICH) is the most deadly and disabling form of stroke. One treatment option is surgical hematoma evacuation; however, two large trials of this intervention have failed to show benefit. The most promising current intervention is minimally invasive surgery (MIS), the subject of the MISTIE III clinical trial. This ancillary protocol, Mechanisms of Tissue Injury in MISTIE III: Rebleeding and Inflammation (MTI:M3) will be an ancillary study to the MISTIE III trial. The overriding goals of this ancillary study are to determine which patients are most likely and least likely to benefit from MIS and whether the level of activation of central nervous system inflammatory mediators is associated with ICH severity, perihematomal edema, and recovery.

### 2. Study Objectives

MTI:M3 will examine neuroimaging together with blood and intrahematomal fluid biomarkers in patients enrolled in MISTIE III. The objectives are as follows: (1) First, we will determine whether the presence of the CTA spot sign, a marker of bleeding risk, can mark those patients at highest risk of perioperative bleeding and lowest likelihood of benefit following MIS. (2) We will determine whether markers of small vessel disease, including cerebral microbleeds (CMB) and white matter hyperintensities, are associated with perioperative complications and opportunity to benefit from MIS. (3) We will determine whether intrahematomal and peripheral markers of inflammation and the cellular immune response are associated with hematoma and intraventricular clot volume, perihematomal edema and outcomes; (4) We will determine whether genetic markers are associated with perioperative complications, the central inflammatory response and outcome following MIS. The results of the proposed study will have direct impact on both clinical care and research. If MISTIE III shows improved outcome after ICH, our results will provide neurosurgeons with the data to determine which patients are the most optimal candidates for the procedure. If MISTIE III does not show a benefit for the overall cohort, our results may still highlight that certain patient subgroups can in fact benefit, and that those patients can be identified in the acute phase. The investigation of intracranial inflammatory cascades in MISTIE III represents a unique opportunity to understand immune responses and potentially identify new targets to limit inflammation and improve outcomes following ICH. Simultaneous analysis of peripheral and central inflammatory responses will for the first time provide direct clinical correlation between the brain and serum inflammatory responses in spontaneous ICH. If an association does exist, then blood surrogates could help gauge the degree of central inflammation.

Overall, MTI:M3 offers a tremendous opportunity to leverage clinical trial data to bring novel insights from ICH pathophysiology into the clinical realm, using neuroimaging, genetic and

inflammatory markers of disease to provide clinicians with powerful new tools to guide surgical therapy and develop new therapeutic targets.

- **Specific Aim 1.** To determine whether CTA spot sign is associated with perioperative bleeding and hematoma reduction after MIS
- **Specific Aim 2.** To determine whether white matter hyperintensity burden and cerebral microbleeds are associated with perioperative bleeding and outcome after MIS.
- **Specific Aim 3a.** To identify the association between acute phase levels of intracranial and peripheral inflammatory mediators and hematoma volume, and perihematomal edema as determined by cerebral imaging.
- **Specific Aim 3b.** To determine whether acute phase levels of intracranial inflammatory markers are associated with 90/180 day functional outcomes in intracerebral hemorrhage.
- **Specific Aim 4a.** To determine if specific genotypes are associated with perihematomal edema and outcome after MIS.
- **Specific Aim 5a.** To determine the cellular immune responses to acute brain hemorrhage and how these responses change over time.
- **Specific Aim 5b.** To determine whether cellular immune responses transition from pro-inflammatory to those that aid in resolution of inflammation are associated with ICH clearance and improved functional recovery.

### 3. Background

Intracerebral hemorrhage (ICH) hematoma size is a potent predictor of poor outcome in ICH. Minimally invasive surgery (MIS) to aspirate and reduce hematoma volume is a promising therapy that may reduce neurotoxicity and brain injury. MISTIE III is a randomized controlled trial examining the relationship between outcome following ICH and MIS. It builds on MISTIE II, which found that one limitation to MIS was variable success in hematoma volume reduction. In some patients, portions of the clot could not be aspirated, or blood re-accumulated, or secondary effects from clot formation may be greater, mitigating the benefit of this procedure. While catheter placement plays a fundamental role, accumulating evidence suggests that patient-specific factors influence the extent of bleeding in ICH and the therapeutic response to ICH surgery.

Our team has demonstrated that contrast extravasation on CT angiography (CTA spot sign) identifies ICH patients at highest risk for hematoma expansion and ongoing bleeding. Furthermore, among patients undergoing surgical hematoma evacuation, CTA spot sign strongly predicted peri-operative and post-operative re-bleeding. Additional genetic and imaging data support the hypothesis that the type and severity of the underlying cerebral small vessel disease associated with ICH will influence outcomes, side effects, and the extent of bleeding. Our team has also demonstrated that in cerebrospinal fluid of patients with spontaneous intraventricular hemorrhage (IVH) treated with external ventricular drainage, maximally elevated mean levels of interleukins, IL-1beta, IL-10 and IL-8 occur on post bleed day

1, which subsequently plateaued around post bleed day 5, before returning to normal by day 10. Levels of monocyte chemo-attractant protein (MCP-1) showed persistent elevation over 2 weeks. The time trends of these markers support experimental data that suggests inflammation is a contributor to acute brain injury after ICH/IVH.

#### 4. Study Procedures

[figure not shown]
MTI:M3 is a prospective and observational, nested study within the MISTIE III randomized controlled clinical trial. This design provides tremendous leverage of the existing workload for MISTIE III, promising major insight into neuroimaging and genetic and inflammatory biomarkers of ICH pathophysiology and response to surgical intervention without affecting the execution of the parent study.

The primary goal of MTI:M3 is to determine whether radiologic and genetic and inflammatory marker data can help identify those ICH patients most likely to undergo successful clot reduction after the MIS intervention and most likely to derive clinical benefit from the procedure. Details of MISTIE III are not reprinted here. Incorporation of MTI:M3 will require an additional informed consent section in the MISTIE III consent for lab draw and collection of hematoma fluid from the collection bag/chamber. All patients enrolled in MISTIE will be eligible for MTI:M3.

- a. The study will be completed as part of the participants' hospitalization and follow-up.
- b. Imaging required for the MTI:M3 study will be done as part of the MISTIE III protocol. Image files will be uploaded to the MISTIE III coordinating center via the electronic data capture system. Image files collected from subjects who also consent to MTI:M3 will then be de-identified and electronically transferred to MTI:M3 investigators for analysis as described below in section 6.
- c. There are 2 types of blood draws:
  - (i) A daily blood draw (two teaspoons, 12 mL) on the day of enrollment into MISTIE III (Day 0) (for both medical and surgical patients) and daily for up to 4 days timed with routine collection of blood for daily blood tests (medical patients), or with hematoma fluid aspiration (surgical patients). Samples will be collected in two separate tubes, one shipped immediately and the other locally processed (centrifuged and aliquoted), frozen at -70°C, and shipped to specific investigators for storage and analysis.
  - (ii) A separate single blood draw (approximately 1 teaspoon, one 6 mL tube) will be collected from medical and surgical MISTIE III subjects at any time during the hospitalization or during follow-up. The 6mL tube of blood will be locally processed (centrifuged and the plasma aliquoted into cryovials) and frozen at -70°C. For sites not able to participate in part (d) below: during this separate blood draw, two additional tubes (10 mL each, approximately 4 teaspoons total) of whole blood will also be collected and frozen at -70°C. The frozen whole blood and plasma from this single draw will be shipped to specific investigators for storage and analysis.

- d. A 1-10 cc sample of the patient's hematoma drainage from the existing brain catheter will be collected on the following schedule:
- (i) At time of initial placement of the brain catheter (at clot aspiration and catheter insertion= "Hematoma aspirate").
  - (ii) Once daily from the drainage bag/collection chamber to be timed immediately prior to injection of rtPA through the brain catheter (= "Drain sampling").
  - (iii) From the drainage bag/collection chamber at the time of removal of the brain catheter.
  - (iv) Samples will be divided and collected in two separate tubes, one shipped immediately and the other locally processed (centrifuged and aliquoted), frozen at  $-70^{\circ}\text{C}$ , and shipped to the specific investigators for storage and analysis.

## Procedures for Perihematomal Fluid Sampling in MISTIE

- e. Additional data collected as part of the MISTIE III protocol will also be made available to MTI:M3 investigators. These data include but are not limited to: study subject ID number, demographic and baseline variables including recent infection

and underlying inflammatory conditions, MIS procedure, rt-PA dosing, outcomes scales scores (blinded data; available after database lock), and adverse events.

## 5. Inclusion/Exclusion Criteria

The participant must be an adult (older than 18 years of age) enrolled in the parent trial for this proposal, MISTIE III.

## 6. Drugs/Substances/Devices

None.

## 7. Study Statistics

- For Aim 1a, to evaluate whether Spot Sign absence predicts clot reduction after MIS, we will analyze clot reduction in two ways: first as a continuous variable compared using a two-sample t-test, then as a dichotomized variable (<60% vs. ≥60%, with ≥60% defined as successful clot reduction) compared using a chi-square test.
- For Aim 1b, we will evaluate whether Spot Sign is associated with increased frequency of neurological complications.
- For Aim 2a, we will evaluate whether white matter disease burden is associated with neurologic complications after MIS.
- For Aim 2b, we will evaluate whether patients with CMBs have less frequent neurological complications.
- For Aim 3a, we will compare serially measured inflammatory markers from serum, and hematoma drainage with ICH, IVH and PHE volumes using standard statistical techniques.
- For Aim 3b, we will assess the association between mean levels of inflammatory mediators and 90/180-day mRS.
- For Aim 4, we will evaluate whether genotype predicts neurological complications after MIS.
- For Aim 5, we will determine the infiltration of peripheral leukocytes into the hematoma and the transcriptional profile of multiple leukocyte subsets in order to determine how leukocyte responses correlate with outcome.

**Data analysis for Aim 1 (Clot reduction and rebleeding).** To evaluate whether Spot Sign absence predicts clot reduction after MIS. Clot reduction will be analyzed in two ways: first as a continuous variable compared using a two-sample t-test, then as a dichotomized variable (<60% vs. ≥60%, with ≥60% defined as a successful clot reduction) compared using a chi-square test. This analysis will focus on the surgical management arm. Based upon prior work, we expect 34% of patients to show a Spot Sign. With a conservative estimate of 30% for the

SD of clot reduction and a sample size of 85 and 165 for Spot Sign positive and negative, respectively, the study will have 80% power to detect a mean difference of 11.3% in clot size reduction. When dichotomized at 60%, the study will have 82% power to detect a difference of 20% (40% for the spot sign positive and 60% for the spot sign negative) with a 0.05 two-sided significance level.

Secondary analyses will include outcomes of severe rebleeding with neurologic deterioration (expected to occur 3.6% of the time), rebleeding into the surgical bed as a radiographic outcome (expected to occur 15% of the time), and bleeding along the MIS catheter tract (expected to occur 30% of the time).

**Data analysis for Aim 1 (Clinical outcomes).** To evaluate whether Spot Sign is associated with improved clinical outcome associated with MISTIE III study intervention.

The primary outcome in MISTIE III is good functional outcome, defined by modified Rankin Score (mRS) of 0-3 at 180 days following treatment. We hypothesize that treatment effect will be more profound among patients who are absent of a Spot Sign. This will be tested using Wald's test for the interaction effect between treatment and Spot Sign in a generalized linear model. The MISTIE III study has 88% power to detect a 13% difference in the dichotomized outcome between the control and intervention group. Our assumptions on the proportion with mRS 0-3 for the four groups are shown in the table below.

	Medial management arm	Surgical management arm
Spot Sign present	18% (N=85)	18% (N=85)
Spot Sign absent	27% (N=165)	44% (N=165)
Total	24% (N=250)	35% (N=250)

With a simulated sample, we found that the study has only 43% power for testing the interaction between treatment and spot sign. However, among the 330 patients without spot sign, the study will have 87% power to detect the 17% difference between treatment arms with a two sided 0.05 significance level.

**Specific Aim 2 (White matter disease burden).** To determine the association between white matter disease burden with successful clot reduction after MIS.

Local MISTIE III sites will electronically transfer MRI images to the MISTIE III coordinating site via the electronic data collection system, which will then be electronically transferred to the MTI:M3 investigators. Specific scanner type and GRE imaging parameters will be documented.

Volumetric analysis of white matter disease will be performed. This analysis will focus on the surgical management arm and white matter disease burden will be compared between those with and without successful clot reduction ( $\geq 60\%$ ) using a two-sample t-test. Assuming 53% of

the patients will achieve successful clot reduction and a SD of 6.9cc, the study will have 80% power to detect a mean difference as small as 2.5cc with a 0.05 two-sided significance level.

**Specific Aim 2 (Microbleeds).** To determine whether patients with microbleeds have a higher likelihood of successful clot reduction after MIS.

Identification of CMBs and determination of their number, size, and distribution will be performed by two trained reviewers blinded to clinical and radiographic information. CMBs will be identified according to criteria proposed by the Microbleed Study Group and in long-term use at the MTI:M3 coordinating center. Briefly, these criteria require that identified CMB be black or substantially hypointense on T2\*-weighted MRI, round or ovoid (excluding tubular or linear structures that may represent flow voids or resorbed macrobleeds), blooming (i.e. larger on T2\*-weighted than spin-echo MRI), devoid of T1- or T2-weighted hyperintensity, and at least half surrounded by brain parenchyma (to exclude primarily subarachnoid bleeding). Our group has previously reported very high inter-rater reliability for detection of CMB using either conventional T2\*-weighted gradient-echo MRI (intra-class correlation coefficient =0.97) or the more sensitive susceptibility-weighted imaging technique (SWI; intra-class correlation coefficient =0.93). Other parameters to be measured on MRI will include the presence of perihematomal edema, extravasation of MRI contrast, and presence of diffusion/perfusion abnormalities. Volumetric analysis of white matter hyperintensity will be performed as previously described, as will evaluation for CAA using the Boston criteria (originally developed by our group).

The primary hypothesis is that presence of CMBs on GRE-MRI is associated with more successful clot reduction. This analysis will focus on the surgical management arm. We predict there will be an association between absence of CMBs, and proportional change in hematoma volume. Similar to Aim 1a above, clot reduction will be analyzed as a continuous variable compared using a two-sample t-test, and as a dichotomized variable compared using a chi-square test. We expect 31% of patients to show signs of CMBs. Assuming a SD of 30% and a sample size of 77 and 173 for any CMBs and no CMBs, respectively, the study will have 80% power to detect a mean difference of 11.6% in clot size reduction. When dichotomized at 60%, the study will have 80% power to detect a difference of 20% (67% for the any CMBs group and 47% for the no CMBs group) with a 0.05 two-sided significance level.

Finally, we propose to evaluate whether the difference in neurologic outcome between the MISTIE III intervention and control is greatest in those with CMBs on GRE-MRI. Secondary analyses will examine the interaction between CMBs, Spot Sign, white matter burden, and neurologic outcome. The model for clinical benefit (i.e. mRS 0-3 vs. 4-6) will include effects for treatment, CMBs, and the interaction between treatment and CMBs. Wald's test will be used to assess the significance of the interaction effect. These results can be confirmed using the CMH test.

**Specific Aim 3a/b.** To identify the association between acute phase levels of intracranial and peripheral inflammatory mediators and hematoma volume, peri-hematomal edema and neurologic outcomes as determined by cerebral imaging and mRS.

The primary outcome measure of this aim is serial levels of inflammatory mediators in hematoma fluid/surgical aspirate. The secondary outcome measures are: (i) ICH/IVH clot burden on admission and end of treatment and absolute/relative perihematoma edema (PHE) at admission and end of treatment (24 hrs post brain catheter removal) compared to time of brain catheter placement; (ii) functional outcomes measured by mRS at 90 and 180 days after admission; and (iii) serial levels of inflammatory mediators in serum. Hematoma aspirate and serum inflammatory markers (see Table below) will be determined by the following methods:

White blood cell count and differential, CRP, glucose, protein, red blood cell count, fibrinogen, and fibrin D-dimer (DD) will be measured using routine laboratory assays.

Concentrations of IL-1 $\alpha$ , IL-2, IL-6, TNF $\alpha$ , IL-8, IL-10, (MCP)-1, (MIP)-1 $\alpha$ , IL-1 receptor antagonist, IL-10, TGF- $\beta$  and IFN $\gamma$  will be quantified using immunoassays.

Levels of matrix metalloproteinases (MMPs) will be assayed by two-step sandwich enzyme-linked immunosorbent assay methods.

Glutamate concentrations will be analyzed by high-performance liquid chromatography.

Inflammatory Marker Studies	
Serum Studies	D-dimer, C-reactive protein (CRP), fibrinogen, matrix metalloproteinases (MMPs), Interleukin-6 (IL-6), tumor necrosis factor- $\alpha$ (TNF- $\alpha$ ), glutamate
Hematoma Aspirate Studies	White blood cell count and differential, glucose, protein, red blood cell count, Interleukin-1 (IL-1), Interleukin-2 (IL-2), Interleukin-6 (IL-6), Interleukin-8 (IL-8), IL-10, monocyte chemoattractant protein(MCP)-1, macrophage inflammatory protein (MIP)-1 $\alpha$ , tumor necrosis factor- $\alpha$ (TNF $\alpha$ ), Interferon-gamma (IFN $\gamma$ ), transforming growth factor(TGF)- $\beta$ , matrix metalloproteinases (MMPs)

Statistical plan: Analysis of categorical variables will be performed using the Pearson's Chi-square test. The Fisher exact test will be used when applicable. Continuous variables will be analyzed using one-way Analysis of variance if data is normally distributed or with Kruskal-Wallis test if not normally distributed. Trend statistic of inflammatory markers will be calculated using the Mantel-Haenszel test for linear association, with the catheter day plotted on the X-axis and levels of specific inflammatory mediators on the Y-axis.

For analysis of secondary outcome measures, inflammatory markers will be expressed as AUC (area under the curve) and included in a multifactorial linear regression model to test for associations with ICH/IVH/PHE volumes and with 90/180-day mRS. The models will include age, sex, and ICH score as covariates. Given the anticipated small sample size of the study population, a total of four or fewer confounders can be controlled in regression models. All tests will be two-tailed, with significance defined by  $p < 0.05$ . Statistical analysis will be performed using STATA 12.0 (Stata, College Station, Texas).

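### Ancillary study, Aim 2 (microbleeds): the CMH test named to confirm the treatment-by-CMB interaction tests the overall treatment effect, so it can neither confirm nor refute the interaction

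*Protocol*

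**What the plan says.** The text is in Protocol Appendix 8 (MTI-M3), Section 7, Specific Aim 2 (Microbleeds). After the clot-reduction analyses it proposes to evaluate "whether the difference in neurologic outcome between the MISTIE III intervention and control is greatest in those with CMBs on GRE-MRI". That is a question about effect modification.

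The model for mRS 0-3 versus 4-6 "will include effects for treatment, CMBs, and the interaction between treatment and CMBs". The test and its confirmation follow: "Wald's test will be used to assess the significance of the interaction effect. These results can be confirmed using the CMH test".

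No homogeneity test is named anywhere in the appendix, and CMH is given no role other than this confirmation. On numbers, Aim 2 states "We expect 31% of patients to show signs of CMBs" and, for the surgical arm, "a sample size of 77 and 173 for any CMBs and no CMBs, respectively". The appendix also cites the parent trial's main-effect power: "The MISTIE III study has 88% power to detect a 13% difference in the dichotomized outcome between the control and intervention group".

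**The concern.** The two tests address different hypotheses. The Wald test asks whether the treatment effect is the same with and without CMBs. CMH, stratified by CMB, asks whether a treatment effect assumed common to both strata is zero. Stratifying by arm instead would test the CMB main effect, which is not the interaction either.

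Agreement between Wald and CMH is therefore not corroboration, and disagreement is not contradiction. Section 2 of the appendix says that the results should show which patients are the best candidates for surgery, and that they may identify benefiting subgroups even if the main trial is negative. In the first setting a chance interaction would very often appear confirmed. In the second a true interaction would often appear unconfirmed. Both follow from the size of the overall effect, not from anything about CMBs.

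**Working it through.** **Inputs**
- 250 patients per arm (Protocol 9.1).
- 77 with and 173 without CMBs per arm. Appendix 8 gives this split for the surgical arm (77/250 = 30.8%); I assume the same for the medical arm.
- mRS 0-3 rates of 25% v 38% (Protocol 9.1.9), and 24% v 35% (the total row of the appendix's spot-sign table). The documents give no mRS rates by CMB status, so all stratum-specific rates below are assumptions.
- Two-sided alpha of 0.05. The appendix states this for the CMB clot-reduction comparison; I assume it for the Wald and CMH tests.

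**The plan's own figure.** Two-proportion power for 25% v 38%, n = 250 per arm, pooled rate 0.315:
- Null SE = sqrt(2 × 0.315 × 0.685 / 250) = 0.04155.
- Alternative SE = sqrt((0.25 × 0.75 + 0.38 × 0.62) / 250) = 0.04114.
- z = (0.13 − 1.96 × 0.04155) / 0.04114 = 1.18, so power = 88.1%, against 88% stated.

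The same formula for 24% v 35% gives 77.1%.

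**What CMH sees.** In stratum k with n_k patients per arm, let a_k and c_k be the good outcomes in the surgical and medical arms, and m_k = a_k + c_k. The CMH numerator is [Σ(a_k − m_k/2)]² = [Σ(a_k − c_k)/2]². With equal arms within strata it depends only on the difference in total good outcomes between arms. How that difference is split between CMB strata drops out. The variance depends only on n_k and m_k.

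**Simulation.** 200,000 trials per scenario; CMH without continuity correction and Wald on the logit interaction. Rates are medical to surgical.

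| Scenario | CMH | Wald | Both | CMH given Wald significant |
|---|---|---|---|---|
| No interaction, 24% to 35% | 77% | 4.9% | 3.8% | 78% |
| No interaction, 25% to 38% | 88% | 5.0% | 4.4% | 88% |
| No effect at all, 25% | 5% | 5.0% | 0.3% | 5% |
| Benefit only with CMBs: 25% to 45%; none without | 34% | 56% | 19% | 33% |
| Opposite effects: 25% to 50% with CMBs; 25% to 14% without | 5% | 99% | 5% | 5% |

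With no interaction, the CMH column is simply the main-effect power computed above. In the last two rows it follows the average effect: 77 × 20 / 250 = 6.2 points, and (77 × 25 − 173 × 11) / 250 = 0.1 points.

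**Fewer patients with MRI.** At an assumed 150 per arm, the no-interaction CMH rate is 68% for 25% v 38% and 54% for 25% v 36%.

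**The case against.** A reader might infer that the plan will usually declare an interaction that does not exist, by setting CMH's 77-88% rejection rate against a nominal 5%. The documents do not support that. The Wald test is the stated interaction test; CMH comes second and is permissive. A false confirmation first needs a false-positive Wald result, and with no interaction that happens in about 5% of trials. Both tests are falsely significant in 3.8-4.4%. This part of the objection stands in full: the error rate of the interaction test is not inflated.

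Three further points deserve weight.
- The high CMH rates require a real overall effect; without one the rate is 5%. This stands.
- The opposite-effects scenario is invented: nothing in the appendix posits harm in patients without CMBs. This also stands, and it is used only as an assumed extreme. The benefit-only-with-CMBs scenario needs no harm, and there CMH still agrees with only a third of true Wald detections.
- If both strata benefit, with more benefit in CMB patients (assumed 25% to 50% and 25% to 33%), CMH is significant in 90% of trials. But the average effect there is (77 × 25 + 173 × 8) / 250 = 13.2 points, and a uniform 13-point effect gives 88%. CMH barely distinguishes the two cases, which supports the point.

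It is also fair that Breslow-Day is nearly the same test as the logit Wald interaction, so naming it would not provide independent confirmation.

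**Conclusion.** The sentence is wrong as written, and nothing elsewhere in the documents corrects it. CMH stratified by CMB carries essentially no information on the interaction. When surgery works overall at the planned size, it agrees with about 77-88% of false-positive Wald results; when there is no overall effect, with about 5%. It can leave a true interaction looking unconfirmed.

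The harm is misleading support or misleading non-support, not an inflated type I error. The rates rest on 250 per arm, a 77/173 split in both arms and the assumed outcome rates. They would change with fewer MRI scans: the ancillary study is optional (Appendix 8, opening paragraph) and MRI is waived in Spain (Protocol 4.3.1 and 5.1). The argument about the hypotheses depends on none of these numbers.

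This is a minor correction. It concerns a secondary analysis in an optional ancillary study and leaves the main trial's primary analysis unaffected.

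**What to change.** In Appendix 8, Section 7, Aim 2 (Microbleeds), either delete the CMH sentence or replace it with a test of the same hypothesis: a likelihood-ratio test of the treatment-by-CMB term, or the Breslow-Day-Tarone test of homogeneity of the treatment odds ratio across CMB strata. Describe it as a check on the Wald result, not as independent confirmation.

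Add that the treatment risk difference with 95% CI will be reported in each CMB stratum and for the contrast between strata. These show the reader the size and direction of any difference, which a second p-value does not.

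If CMH is kept, label it only as a CMB-stratified test of the overall treatment effect.

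The cost is one or two sentences in the appendix, with no new data.
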